### **D2.4 Anticipated Results:**

We anticipate that the bihemispheric stimulation ( anodal on the lesional hemisphere and cathodal stimulation on the non-lesional hemisphere) will induce the largest increase in the cortical excitability in the lesional hemisphere compared with the other two stimulation montages – anodal stimulation on the lesional hemisphere only or cathodal stimulation on non-lesional hemisphere only.

### **D3.1 Limitation, Potential Pitfall and Alternative Approach:**

- Why not perform these studies in healthy subjects first? We are pursuing a similar study in healthy subjects through other funding mechanisms. However, the information from healthy subjects can not be applied to stroke patients because they are completely different populations. In general, there is a concern for potential increased risk for stroke patients for tDCS stimulation.
- We are testing for effects and safety with a single session, but the treatment studies would likely involve multiple tDCS sessions? Feasibility, unlikely to see cumulative safety issues over multiple sessions.
- If the difference of induced cortical excitability between different electrode stimulation montage is smaller than expected, the alternative approach is to increase sample size or consider multiple sessions rather than single session.

#### **D4. 1 List of Protocols:**

##### **MRI Protocol:**

Study subjects will be scanned at the Center of Advanced Imaging (**NI core**) by a Siemens 3T Trio MRI scanner using a standard radiofrequency head coil at before and within 2 hours after stimulation. During MRI, electrode positions will be marked by placing vitamin pills detectable in MRI scans at the center of the tDCS electrodes. Areas of 3\* 5 cm, which were the size of the tDCS electrodes, will be determined as regions of interest (ROI) around this center for the stimulated primary motor cortex. Head motion will be minimized by foam padding and forehead-restraining straps if necessary. T1 contrast enhanced weighted anatomical\_image (IR/TR/TE = 1100/1900/3.37; resolution = 1 x 1 x 1 mm^3; FOV = 256 x 256), Fluid attenuated inversion recovery (FLAIR, TR/TE = 9000/89; resolution = 0.43 x 0.43 x 5 mm^3; FOV = 220 x 192.5) and DWI (TR/TE = 5.5 s/99 ms; resolution = 3 x 3 x 3 mm^3; FOV = 222 x 222). In T1- diffusion-weighted studies, and ADC maps will be visually inspected for signal changes by a blinded board certified neuro-radiologist or neurologist. Furthermore, pixel by-pixel subtraction of the post-stimulation ADC parametric images from the baseline ADC parametric images will be performed by means of an implemented scanner software algorithm for improved differentiation and highlighting of possible locally restricted ADC changes. Statistical difference between the ADC values before and after stimulation will be calculated and analyzed.

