#### **Aim 1: To determine the optimal tDCS current in stroke subjects**

The optimal current balances cortical excitability and tolerability/safety in stroke patients. We will investigate the optimal current in range of 1 mA to 4 mA. We hypothesize that 4 mA is tolerable, safe and can induce the highest level of cortical excitability in the lesional motor cortex. We will adapt the classic, gold-standard 3+3 experimental design that is commonly used to find the maximal tolerable dose in drug trials. Tolerability/safety will be investigated by monitoring clinically detectable symptoms by monitoring vital signs and surveying subjects with a questionnaire before and after stimulation, additionally by detecting subclinical neuronal injury using (1) Magnetic Resonance Imaging/Diffusion Weighted Imaging (MRI/DWI) to detect any focal ischemia; and 2) Molecular biomarkers: S100b and neuron-specific enolase (NSE) to detect neuronal injury. Cortical excitability is measured by the amplitude of motor evoked potentials (MEPs) induced by TMS from the abductor pollicis brevis muscle of the affected side.

**What is the optimal tDCS electrode montage for stimulation?** According to the theoretical model underlying the use of tDCS for stroke motor recovery, stroke causes an “interhemispheric imbalance” with decreased motor excitability in the ipsilesional hemisphere and excessive excitability in the contralesional hemisphere. This has led to studies testing the effects of anodal (excitatory) stimulation to the lesional hemisphere, cathodal stimulation (inhibitory) to the non-lesional hemisphere or combined bi-hemispheric stimulation. However, it has not been established which montage can induce the maximal cortical excitability, and eventually the maximal motor recovery.

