**B. Innovation:**

- Innovative trial design.** We innovatively adapt a 3+3 trial design (**Figure 4**) that is commonly used in drug trials to assess safety and tolerability of tDCS current for Aim 1. Current associated with tDCS technique is like dosage to a drug that can be adjustable. Evaluating safety/tolerability of tDCS technique is similar to assessing drug safety and dosing finding. While innovative, the design is simple and easy to understand as well as to implement.
- Use of MR imaging and biomarkers to test for subclinical neuronal injury.** We will test for subclinical injuries with a combination of imaging and biomarker measurements to best ensure the safety in stroke subjects, as opposed to only assessing safety and tolerability with clinically detectable symptoms as done in most of the previous tDCS safety studies. MRI Diffusion Weight Imaging, dependent on the motion of water molecules, provides information regarding tissue integrity. It is a gold standard for early detection of brain ischemia  with a high sensitivity as well as high specificity . An Apparent Diffusion Coefficient (ADC) value decrease represents diffusion restriction while an ADC value increase indicates an increase in water mobility in the stimulated cortex. Neuron-specific enolase (NSE) and S-100b protein (S-100b) are two widely investigated molecular markers for brain injury . NSE originates from the cytoplasm of neurons and neuroendocrine cells. S-100 protein is a dimeric acidic calcium-binding protein found in the brain with high concentrations in astrocytes and Schwann cells. The serum levels of these proteins are elevated after different types of brain injury including focal and global ischemia , traumatic brain injury  and hypoxic brain injury .

[figure not shown]

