### **Definition of Major Response and “Stopping Rule”:**

A major response is defined by any of the following serious adverse events occurring during the study period. It serves as the “stopping rule” as detailed in the **Figure 4** above.

- Second degree scalp burn at the site of electrode pad; or
- Seizure; or
- New lesion(s) on DWI sequence of MRI scan and the lesion(s) is not explained by any other cause(s) or decreased ADC under the electrode stimulating motor cortex area; or
- Patient discontinues from the study due to any reasons above.

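### The MRI protocol calls the T1 image at both Aim 1 scans contrast enhanced, but the visible exclusions, risk text and procedure steps contain nothing specific to contrast

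*Combined protocol and SAP*

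**What the plan says.** The MRI Protocol in section D4.1 is the operative scanning text. Steps 9 and 20 of D1.2 call the scan a structural 3T MRI and send the reader there and to the imaging core for details. It gives one list of sequences (a "T1 contrast enhanced weighted anatomical" image, FLAIR and DWI) for scans made "at before and within 2 hours after stimulation". Table 2 marks Brain MRI both before and after stimulation.

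The imaging purposes stated elsewhere are these:

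- Aim 1 names "Magnetic Resonance Imaging/Diffusion Weighted Imaging (MRI/DWI) to detect any focal ischemia", and B. Innovation gives the rationale: "MRI Diffusion Weight Imaging, dependent on the motion of water molecules, provides information regarding tissue integrity".
- The imaging items in the stopping rule are "New lesion(s) on DWI sequence of MRI scan" (if not otherwise explained) or "decreased ADC under the electrode stimulating motor cortex area".
- The planned imaging statistic is on ADC: "Statistical difference between the ADC values before and after stimulation will be calculated and analyzed".
- The MRI Protocol also uses the scans to locate markers at the electrode centres and to set the regions of interest. The TMS protocol uses an anatomical MRI to guide the coil.
- The MRI Protocol says "In T1- diffusion-weighted studies, and ADC maps will be visually inspected for signal changes". The sentence is garbled but appears to include the T1 images.

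On screening and risk, the Exclusion Criteria itemise shared MRI, tDCS and TMS risk factors: implants, loose metal, pregnancy, seizure history, and scalp or bone defects. The MRI risk text covers field strength, metal, claustrophobia, noise, hearing and discomfort. The MRI paragraph under Protection to Human Subjects excludes anyone with an MRI contraindication by means of a screening form whose items are not shown.

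**The concern.** A scanning protocol tells staff what to acquire. If it names a contrast-enhanced image, one expects the agent and dose, a step at which it is given, a matching exclusion and a line of risk text. The visible plan has none of these. Either the phrase is wrong or the supporting provisions are missing from the places where a reader would look.

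What is at stake is a small matter of patient safety and clarity. Followed to the letter, the plan would give contrast twice in one day with no contrast-specific screening or risk statement in the text we have. In practice nobody could inject from this sentence alone, so the likely effect is a query, or a decision made locally and not in the protocol.

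Reading the same steps shows a second, separate matter of ordering. Pregnancy is listed among the shared MRI, tDCS and TMS risk factors, yet the stimulation-day pregnancy test comes after the first scan.

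**Working it through.** The plan has no figure of its own to reproduce on this point. The check sets the sections side by side, with two short pieces of arithmetic.

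**1. Does the wording apply to both scans?** The MRI Protocol gives one sequence list for the scans before and after stimulation, and Table 2 marks both. As written, yes.

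**2. Does it apply to Aim 2?** No. The Aim 2 recruitment section carries over the TMS, tDCS and rehabilitation protocols only, and Table 3 has no MRI row.

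**3. What supports contrast in the visible text?**

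| Place | Content bearing on contrast |
|---|---|
| MRI Protocol, D4.1 | Names the sequence; the bracket gives acquisition parameters only, with no agent, dose or route |
| D1.2, steps 9 and 20 | Structural 3T MRI, 30 minutes each, with a reference to the MRI protocol; no injection step |
| Exclusion Criteria | Five itemised risk factors, none specific to contrast |
| Potential Risk, MRI | Nothing on a contrast agent |
| Protection to Human Subjects, MRI | General contraindication by form; items not shown |

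**4. Would removing the phrase conflict with anything?** The stopping rule's imaging items rest on DWI and ADC, and the planned statistic is the ADC difference. Neither refers to contrast. Marker location, the regions of interest and coil guidance are also described without reference to contrast. The one place where contrast might matter is the visual inspection, which appears to take in T1 images. That is why intent cannot be settled from the text.

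**5. Reach of the wording.** Scans covered = 2 × number of Aim 1 subjects. D1.3 predicts 18 subjects and gives a theoretical range of 3 to 36.

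- Predicted: 2 × 18 = 36 scans
- Range: 2 × 3 = 6 to 2 × 36 = 72 scans

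These counts show how far the sentence reaches. They are not expected injections and do not measure harm.

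**6. Pregnancy test order in Aim 1.** The baseline test is at step 3, the first MRI at step 9, the stimulation-day test at step 11 and tDCS at step 15. Table 2 places baseline at Day -7 ± 7:

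- Earliest: -7 - 7 = Day -14
- Latest: -7 + 7 = Day 0

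At the first MRI the most recent test can therefore be 0 to 14 days old. The second test precedes tDCS but not the scan. When baseline is on the same day, which the Table 2 footnote allows, there is no gap. The plan does not say how many women this concerns.

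**The case against.** The strongest reply is that everything hangs on one garbled phrase in a section with other broken sentences. It may be a slip, an editing remnant, or a loose description of a T1-weighted image, since only sequence parameters follow it. The steps refer to imaging core documents that we do not have, the screening form may ask about contrast, and some pages were removed. All of this stands. It means the documents do not show that contrast is intended, and deletion should not be the default before the sponsor has answered. It does not remove the mismatch: the visible exclusions and MRI risk text are detailed and contain nothing on contrast.

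Some stronger readings are tempting, but the documents do not support them:

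- *Subjects receive contrast without being screened or told.* The consent pages were removed and the form's items are not shown.
- *The stopping rule should list a contrast reaction.* That rule defines responses that limit the current, so its silence on contrast is no defect.
- *The structural 3T MRI label contradicts the MRI Protocol.* It defers to that protocol and does not exclude contrast.
- *The blood draws show that no injection was planned.* The venipuncture text counts three draws, while the Laboratory Protocol lists four serum times, so this account is not firm enough to argue from.

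On the pregnancy test, a reader might infer that pregnant women would be scanned unchecked. The text does not support this. A baseline test precedes the scan, and the tDCS risk text has women of childbearing age questioned before each session. The stated reason for excluding pregnancy is also tDCS, and the second test already comes before it.

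**Conclusion.** The mismatch is real and minor. The MRI Protocol describes the T1 image at both Aim 1 scans as contrast enhanced, while the itemised exclusions and MRI risk text make no specific provision for contrast and no agent, dose or injection step is given. Confidence is high about this silence in the visible text. It is not high about intent, which the documents leave open.

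The conclusion assumes that the supplied text is the current plan and makes no claim about the consent form, the screening form or the imaging core documents. It concerns Aim 1 only. No endpoint, sample size, escalation decision or analysis changes.

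The order of the pregnancy test is a small improvement on offer, not an error in the plan.

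**What to change.** Ask the sponsor to state whether contrast is intended, then amend the text to match.

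- **If not intended:** in the MRI Protocol, drop the two words that refer to contrast so that the item reads T1-weighted anatomical image.
- **If intended:** name the agent and dose, and add an injection step at steps 9 and 20, a contrast-specific item in the Exclusion Criteria, and a contrast risk in the MRI risk text.

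The first route costs two words. The second costs a few lines and some screening work, which contrast would need in any case.

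Separately, move the existing Aim 1 stimulation-day urine pregnancy test from step 11 to before the MRI at step 9, so that a subject found ineligible that day is not scanned first. This adds no test. The subject could stop first at the QBAR laboratory, which step 10 puts under 100 yards from the imaging centre. Testing at the imaging centre would also serve, but the plan does not say whether that is feasible.

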##### **Laboratory Protocol:**

The laboratory test will be processed and analyzed at [name] lab in the Children's Hospital. The serum samples will be collected at baseline, before stimulation, after stimulation and one week after stimulation. The samples will be centrifuged at 3000 rpm for 10 min and stored at -20 °C prior to the analyses. The NSE assays will be performed using a radioimmunoassay technique (Cobas Core NSE EIA, Hoffmann-La Roche, Switzerland). The S-100b concentrations will be measured by an immunoluminometric assay for the quantification of protein (LIAMat® Sangtec®100, Sangtec Medical, Sweden). The sensitivity of the S-100b assay will be 0.02 µg/l.

##### **TMS protocol:**

The TMS evaluation will be conducted at the Brain Stimulation Laboratory (**BSTIM Core**) and performed by trained research staff members who are blinded to the study. Subjects will be seated comfortably in a chair specifically designed with a chin rest, head rest and molded armrest in which they could keep their arms in a constant relaxed position. Subjects have 9mm Ag/AgCl surface electrodes placed over the abductor pollicis brevis (APB) muscle. The TMS coil will be positioned using a neuronavigational guidance system (Brainsight™, Rogue Research Inc., Montreal Quebec) along with the participant's MRI. Given that neuroanatomy is often shifted post stroke, this system will allow us to maximize precision of the coil placement. The stereotactic guidance system consisted of trackers attached to the TMS coil and to the subject's head which could be detected by an optical position sensor. Following a calibration procedure, these trackers are monitored by the

software which displayed the position and orientation of the coil on the subject's anatomical MRI scan. This technique facilitates repeated positioning of the TMS coil over the subject's brain. The location of the motor area governing the thumb is isolated for each individual by moving the TMS coil in 0.5 cm steps to find the site at which the maximum twitch could be elicited. EMG signals are recorded using a closed-loop system, in which feedback from the EMG is used to control the output of the TMS machine via specially written scripts (Spike software, Cambridge Electronic Design, Cambridge, UK). The raw EMG signal is amplified and bandpass filtered (low-pass = 0.5 Hz, high-pass = 1 kHz) using the CED 1902 Quad-System (Cambridge Electronic Design Limited, Cambridge, U.K.). It is digitized (sampling rate = 5 kHz) and recorded onto a PC using Spike software and a Micro 1401 data acquisition unit (Cambridge Electronic Design Limited, Cambridge, U.K.). The resting motor threshold (rMT) is determined using a procedure known as the maximum-likelihood strategy in which the parameter estimation by sequential testing (PEST) algorithm is used. The PEST method uses the EMG response to the TMS pulse to determine if TMS intensity needs to be increased or decreased. In our closed-loop system, the TMS machine is automatically adjusted according to PEST output, resulting in an MEP of 50  $\mu$ V in 50% of trials. Thus, the rMT is determined in a matter of minutes, is much less labor intensive compared with the Mills-Nithi IFCN method and less prone to human error. Cortical excitability was tested by delivering 10 TMS pulses to M1 of each hemisphere (TMS intensity of 20% above the individual rMT to induce MEPs of at least 1 mV, if MEPs size is smaller than 1mV, then TMS intensity will go up to 100% and kept at 100%). The same intensity was kept constant pre and post-stimulation. Ten MEPs will be recorded for each hemisphere, and their peak-to-peak amplitude will be averaged to determine MEPs amplitude.

#### **tDCS Protocol:**

Direct current stimulation will be delivered to the study subjects through 2 saline-soaked EasyPad (3cm \* 5cm=15cm^2) using a Chattanooga Dual-Channel Iontophoresis Device (Chattanooga Medical. Inc). For this protocol, the bihemispheric stimulation montage will be used because a safety profile can be evaluated for both anodal stimulation and cathodal stimulation on the same subject. The anodal stimulation will be placed over the ipsi-lesional and the cathodal over the contra-lesional motor cortex (C3 and C4 areas by using the international 10 –20 EEG electrode systems). Electrode pads will be disposed after each stimulation session. During the middle of stimulation, an inspection of electrode pads will be conducted to make sure they have not dried out, and the scalp temperature will be measured using a touchless thermometer. Stimulation will last for 30 minutes. Thus, subjects will perform for thirty minutes with stimulation and 30 minutes after it has ended. The QBAR core therapist will be blinded to dosage and montage of stimulation by the BSTIM core technician. The experiment will be conducted in the Upper Extremity Function Laboratory of the Center for Rehabilitational Research in Neurological Conditions (**QBAR core**).

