#### Aim 1: To determine the optimal current in stroke patients

##### D1.1 Design:

This aim is a phase I type study to determine the most efficacious current for tDCS, recognizing that this current level must be tolerable and safe. The trial design is adapted from the classical, gold-standard 3+3 drug trial design, which is commonly used to find the maximal tolerable dose for a chemical drug. The main justification for this design is that the maximal tolerable current (dose) is usually and arbitrarily defined as the dose at which one-third of the patients experience current (dose)-limiting major side effects/response. The algorithm for current (dose) escalation is detailed in (**Figure 4**). The study starts with 1 mA : (a) if no major response occurs in any of the three subjects, a next current at 2 mA will be used next; (b) if major response occurs in 2-3 study subjects, then the trial will stop at this current level; (c) if major response occurs in one subject, then 3 additional study subjects will be entered to further test the safety of same current dose; if no major response occurs, then the current will be escalated next current level; if further major response occurs, then the trial will terminate. The previous current level will be defined as the maximal tolerable current (dose). The current tDCS device available on the market (Chattanooga Dual-Channel Iontophoresis Device) for research use has a maximal current of 4.0 mA. The sequence for current escalation will be 1.0 mA >> 2.0 mA >> 2.5 mA >> 3.0 mA >> 3.5 mA >> 4.0 mA.

While we vary current in this protocol, other features of the stimulation will be controlled:

- **Duration of stimulation will be 30 minutes:** Data show the increased excitability of tDCS can last as long as 90 minutes. Our rehabilitation intervention will take one hour. Thus, by using 30 minutes of

stimulation, as has been commonly used in stroke studies, we should ensure that the potentially beneficial effects of the stimulation will not wear off during the course of rehabilitation.

- **Size of electrode will be 3 × 5 cm^2:** The commonly used 3 × 5 cm^2 size pad is chosen because it is adequate to cover the the primary motor cortex – our area of interest for brain stimulation in stroke subjects to facilitate upper extremity motor function recovery.

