25. Note that these analyses must be completed for each set of 3 subjects in a group to determine whether one or more major responses occurred before enrollment continues. If no major response occurs, the next 3 subjects will be entered to go through procedure 9-23 according to **Figure 4**.

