### **D1. 3. Statistical Analysis:**

Due to the nature of 3+3 design (**Figure 4**), the theoretical sample size varies from 3 to 36 depends on when the trial stops under "stopping rule". However, we hypothesize that no major responses will occur at any current (dose) level and the current will be escalate to 4 mA, thus we predict that 18 stroke subjects will be required for Aim 1. First, patients' demographic and clinical characteristics will be summarized. Summary statistics for continuous variables includes number of subjects, means, median and standard deviations. Summary statistics for discrete variables includes counts and percentages for each category. Secondly, the safety measures will be summarized by current(dose) group with descriptive statistics. Thirdly, a current(dose) response curve will be plotted by MEPs amplitude versus current (dose) groups. Per DSMB recommendation, S-100 and NSE will not used as a stopping rule, however, they will be still collected and analysed separately and presented to DSMB meeting. The statistical analyses will be performed with SAS V9.2 (SAS Institute Inc., Cary NC).

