### **D5.5 Additional information about recruiting patients from research database:**

Subjects with stroke will be recruited from the recruitment database maintained at the MUSC Center for Rehabilitation Research in Neurological Conditions (CRRND) which is housed in the CHP Department of Health Sciences and Research (secondary appointment of the PI and primary appointment of the research therapist). The research database (approved MUSC IRB #15991) currently contains ~200 persons with stroke who have signed informed consent and agreed to be contacted for research participation. The research

database is managed by a designated coordinator. This coordinator will be provided with the inclusion/exclusion criteria for the current study. This study will also recruit from the Registry for Stroke Recovery (RESTORE-Pro#00037803), which is a registry with subjects consented for future contact. RESTORE staff will query the registry for potential subjects and provide the Principal Investigator (PI) with the contact information of subjects who meet their criteria. The PI or research staff will contact subject to further screen for potential enrollment. When a potential participant is identified that meet inclusion criteria the PI, project coordinator or research therapist will contact participants by phone to determine if they want to participate in the current study. If they wish to participate they will be scheduled for a time for the PI, project coordinator or research therapist to obtain informed consent for the study proposed. Consent will be obtained after reviewing the protocol and consent form with each potential subject. If a potential subject is deemed unable to participate in informed consent, consent will be obtained from a relative with the patient present. For patients consenting themselves, every attempt will be made to have a relative present during the informed consent. The MUSC IRB will approve the informed consent form.

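### Aim 1 claims blinding to current, but its fixed ascending ladder makes the current largely predictable and no concealment is described, so the MEP-by-current curve should be read as open-label

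*Combined protocol and SAP*

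**What the plan says.** Two statements in section D4.1 claim blinding that bears on Aim 1. The tDCS Protocol says: "The QBAR core therapist will be blinded to dosage and montage of stimulation by the BSTIM core technician". The TMS protocol says the evaluation is "performed by trained research staff members who are blinded to the study". Neither says how the current is concealed.

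The allocation of current is set elsewhere:

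- D1.1 fixes the order: "The sequence for current escalation will be 1.0 mA >> 2.0 mA >> 2.5 mA >> 3.0 mA >> 3.5 mA >> 4.0 mA". Three subjects are treated at a level, and "if no major response occurs in any of the three subjects, a next current at 2 mA will be used next". One major response adds three more subjects at the same current.
- D1.2, step 25, makes the cohort boundary visible: "these analyses must be completed for each set of 3 subjects in a group" before enrolment goes on.
- D1.2, steps 15 and 17, have the PI give the stimulation under BSTIM Core oversight, and a BSTIM Core technician record the MEPs after the therapy hour.
- D5.2 says the TMS assessment is done by a research assistant together with the applicant.

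On use of the data, D1.3 says "a current(dose) response curve will be plotted by MEPs amplitude versus current (dose) groups", and D1.4 expects the largest MEP increase at 4.0 mA. The sentence declaring subjects, therapist and assessor all blinded stands only under Aim 2, where montage order is randomised.

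**The concern.** Aim 1 does two jobs. One is a tolerability decision, for which an open 3+3 is usual. The other is to find the most efficacious current (D1.1), using the MEP-by-current curve. Its result sets the current for Aim 2 and for the planned follow-on trial (D5.4), and the first manuscript is to report efficacy by current level (D5.1, Table 1).

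The team has stated which current it expects to do best. If those who deliver therapy or record MEPs know the current, expectation can enter the outcome between the pre and post recordings. A curve reported as blinded would then carry more weight than the design supports.

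**Working it through.** **1. The plan's own figures.** D1.3 gives a range of 3 to 36 subjects and predicts 18. The D1.1 rule has six levels:

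- minimum: stop at the first level = 3;
- no major response: 6 × 3 = 18;
- every level expanded: 6 × 6 = 36.

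All three are reproduced.

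**2. What enrolment order reveals on the predicted path.** For subject k the level is k/3 rounded up. Subjects 1–3 receive 1 mA, 4–6 receive 2 mA, 7–9 receive 2.5 mA, 10–12 receive 3 mA, 13–15 receive 3.5 mA and 16–18 receive 4 mA. The current is identified for 18 of 18. A guess without order would be right 1/6 = 17% of the time.

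**3. What order reveals if cohorts are expanded.** Suppose only the 2 mA cohort is expanded (21 subjects) and the observer does not know it. The rule, capped at level 6, is right for subjects 1–6 and 19–21, that is 9 of 21 = 43%. It is one level too high for the other 12.

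In general, let p be the probability of a major response per subject, taken as equal at all levels. The documents give no p, so 0.01 to 0.20 is an assumed range. The chance of no major response in 18 subjects is (1 − p)^18. The other columns come from 20,000 simulated runs of the 3+3 rule.

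| p | (1 − p)^18 | Exact current from order alone | Within one level |
|---|---|---|---|
| 0.01 | 0.83 | 93% | 99.9% |
| 0.02 | 0.70 | 88% | 99.5% |
| 0.05 | 0.40 | 74% | 98% |
| 0.10 | 0.15 | 63% | 95% |
| 0.20 | 0.02 | 54% | 91% |

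An observer who also knows which cohorts were expanded is right every time, at any p. A burn or seizure in the session would be plain to staff; an expansion prompted only by an MRI finding might not be.

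**4. Who knows the current, whatever the order.** Set side by side:

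- D1.2 step 15: the PI administers the current; BSTIM Core oversees.
- D1.2 step 17: a BSTIM Core technician records the post-stimulation MEPs.
- tDCS Protocol: a BSTIM Core technician keeps the therapist blind, which suggests that this technician knows the current. The documents do not say whether this is the technician of step 17.
- D5.2: the applicant takes part in the TMS assessment.
- TMS protocol: those doing the assessment are blinded.

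If the applicant is the PI, as I read the documents, the person giving the current also takes part in measuring its effect. That conflicts with the TMS protocol without any argument from enrolment order.

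**5. Size of any bias.** The documents give nothing from which to estimate it. As illustration only, take three normal responses per level (SD 1), no true effect, and an assumed expectation-driven drift, linear by level, totalling 0, 0.25, 0.5 or 1.0 SD. The 4 mA mean is then highest in 17%, 22%, 29% or 41% of simulated trials. These figures restate the assumed drift; they are not evidence about this trial.

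**The case against.** The strongest reply is that predictable does not mean known. Order reveals the current only to someone who knows the ladder, the subject's position and any expansion. The documents do not say that one therapist or technician sees every subject in turn. This stands, so a reader who infers that blinding cannot hold, or that all 18 currents are always known, goes further than the text; that is exact only on the no-response path.

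Second, the therapist records no MEPs. That also stands. The therapist matters only because the therapy hour falls between the two recordings. The more direct conflict concerns the TMS assessors (step 4 of the working).

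Third, the TMS protocol has real safeguards: neuronavigated coil placement, closed-loop threshold finding, the same intensity before and after, and ten averaged peak-to-peak amplitudes. These limit observer influence. They leave the hotspot search in 0.5 cm steps and coil handling to the operator. The blinded MRI reading protects a safety endpoint, not the curve.

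A reader might also infer that the PI could choose whom to place at the next current, because "The PI or research staff will contact subject to further screen for potential enrollment". The documents describe no queue to choose from, plan accrual of only 2–3 subjects a month, and do not show that baseline results predict MEP change. I do not press this route. Nor do they show that the curve is in fact biased towards 4 mA. D1.3 plans a plot without a test, so no error rate is inflated.

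**Conclusion.** The point holds in a limited form. The current in Aim 1 is largely predictable from enrolment order: for 18 of 18 subjects on the predicted path, and for 54% to 93% exactly (91% or more within one level) if expansions occur unknown to the observer. The latter range rests on an assumed p of 0.01 to 0.20, equal across levels. No concealment is described, and D1.2 and D5.2 together bring the person delivering the current into the outcome assessment, assuming PI and applicant are the same person.

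The stated blinding is therefore not reliably a property of Aim 1, and the MEP-by-current curve should not be presented as blinded. The size of any resulting bias is unknown. The 3+3 tolerability decision is largely unaffected, and the enrolment-order argument does not reach montage: it is the same for everyone in Aim 1, and its order is randomised in Aim 2.

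**What to change.** Three changes, none touching the ladder, the stopping rule or the sample size:

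1. Reconcile D1.2 (steps 15 and 17), the TMS protocol, the tDCS Protocol and D5.2. State that Aim 1 is effectively open as to current, and that the D1.3 curve is read as open-label and exploratory. Staff may still not be told the current; that precaution is harmless and can stay.
2. Have the MEPs acquired by existing BSTIM staff who neither set nor administer the current, and amend D5.2 to match.
3. Before the D1.3 curve is drawn, measure the stored APB traces from coded files with subject and pre/post order hidden, and use those amplitudes.

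The cost is protocol wording, a less favourable blinding statement, a coded export of recordings already digitised, and a few hours of measurement. Coded measurement cannot remove bias that arises while the MEPs are being acquired, which is why the second change is needed as well.
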